2. RESEARCH DESIGN AND METHODS

This is a multi-center, non-randomized, single-arm, prospective trial designed to evaluate the safety of a novel 1.1mm single-use flexible cryoprobe with oversheath. Consecutive patients who have been referred for transbronchial biopsy by their treating pulmonologists will be enrolled. Transbronchial biopsy will be performed using the ERBE 1.1mm single-use flexible cryoprobe with oversheath together with the ERBECRYO 2 unit.

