2.1. OBJECTIVE AND PURPOSE

The objective of this study is to evaluate the safety profile of the new 1.1mm single-use flexible cryoprobe with oversheath for the sampling of lung tissue. The safety profile will be assessed across the

various indications for transbronchial lung biopsy (i.e. lung transplant rejection surveillance, lung nodule biopsy, diffuse parenchymal lung disease, pneumonitis). Safety will be assessed by collecting AE and SAE information up to 30 days.

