2.3. SECONDARY ENDPOINTS

Secondary Outcomes will include (for definitions, see Data Collection):

- 1) Mild or Moderate Adverse Events: Rate of bleeding grade ≤ 2 , pneumothorax not requiring chest tube placement (Grade 1)
- 2) Histologic Accessibility Grade
- 3) Total Histologic area (mm^2)
- 4) Alveolated Area (mm^2)
- 5) Open alveoli percent
- 6) Percent crush artifact
- 7) Artifact free lung parenchyma percent
- 8) Activation time
- 9) Diagnostic Yield: defined as proportion of patients for which the cryobiopsy sample led to a specific diagnosis on histologic examination
- 10) Procedure time

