- Grade 1: Due to very poor specimen quality, it is not possible to assess the relevant morphologic and histologic features
- Grade 2: Due to poor specimen quality, assessment of relevant morphologic and histologic structures and features is severely compromised and not possible
- Grade 3: Despite high limitations in specimen quality, assessment of the relevant morphologic and histologic structures and features is severely compromised but possible
- Grade 4: Despite moderate limitations in specimen quality, assessment of the relevant morphologic and histologic structures and features is compromised but possible
- Grade 5: Despite low limitations in specimen quality, assessment of the relevant morphologic and histologic structures and features are compromised but possible

- Grade 6: The specimen allows for complete and unrestricted assessment of all relevant morphologic and histologic structures and features

Additionally, the pathologic core lab will determine, the total histologic area (mm²), alveolated area (mm²), open alveoli percent, percent crush artifact, and artifact free lung parenchyma percent. The underlying diagnosis will be confirmed or rebutted.

▪ *Diagnostic Yield:*

Diagnostic yield is defined as proportion of patients for which cryobiopsy led to a diagnosis. Diagnostic yield will be determined from the results of cryobiopsy specimen only. A biopsy that results in a specific diagnosis, either malignant or benign (granuloma, inflammation, fibrosis, infection) will be assumed to be a true positive. Atypia, minimal inflammation or lung parenchyma without pathologic findings on final pathology reads are considered non-diagnostic.

▪ *Room Temperature and Gas Pressure:*

The room temperature of the OR (by a thermometer fixed to the ERBECRYO 2 unit) and the gas pressure which is displayed on the cryo unit will be collected prior to the index procedure. This ensures standardized results throughout the study. The gas pressure and the room temperature must be at least 56bar and 68°F (20°C), respectively.

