5.2. STATISTICAL HYPOTHESES

1. To determine the serious adverse event rate of a 1.1mm flexible single-use cryoprobe with oversheath for transbronchial bronchoscopic biopsy.

We hypothesize that the serious adverse event proportion using the novel smaller, 1.1mm flexible single-use cryoprobe with oversheath will not exceed 30%, the adverse event proportion for the current standard method of transbronchial biopsy using forceps.

2. To determine baseline performance characteristics for the use of the 1.1mm flexible single-use cryoprobe with oversheath.

We hypothesize that data generated during the performance of this safety trial will generate meaningful descriptive statistics for pathologic evaluation (histologic adequacy), procedural characteristics (activation time, number of biopsies taken, type of airway used), and diagnostic yield across various disease states necessitating transbronchial biopsy. This descriptive data will be crucial in the planning of future clinical trials.

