5.4.3. ANALYSIS OF THE SECONDARY ENDPOINTS(S)

1. Description of histologic performance. The mean histologic adequacy score, total histologic area (mm²), alveolated area (mm²), open alveoli percent, percent crush artifact, and artifact free lung parenchyma percent will be reported as mean (+/- SD) or Median (Range). This data will be used for statistical planning for future trials.
2. Procedural characteristics such as activation time, procedure time, number of biopsies taken and type of airway (proportion used LMA, ETT, rigid bronchoscope) used will be reported as mean (+/- SD) or Median (Range). Logistic regression will be used to determine if procedural characteristic significantly affect the presence of a significant adverse event (primary outcome). Additionally, linear regression will be used to determine if any of the procedural characteristics effect histologic performance characteristics.
3. Diagnostic yield of cryobiopsy will be calculated as the proportion of patients for which cryobiopsy led to a specific diagnosis. A biopsy will be considered diagnostic, if it results in a specific diagnosis, either malignant or benign (granuloma, inflammation, fibrosis, infection) will be assumed to be a true positive.

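### Diagnostic yield scores a normal transplant-surveillance biopsy as non-diagnostic, and 5.4.3 gives neither a rule for these patients nor the split by disease state that 5.2 intends

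*Combined protocol and SAP*

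**What the plan says.** Diagnostic yield is defined in three places, each time as a single proportion of patients. Section 2.3 has it "defined as proportion of patients for which the cryobiopsy sample led to a specific diagnosis on histologic examination". Section 3.6 states "Diagnostic yield is defined as proportion of patients for which cryobiopsy led to a diagnosis" and then lists what does not count: "Atypia, minimal inflammation or lung parenchyma without pathologic findings on final pathology reads are considered non-diagnostic". Section 5.4.3 gives the analysis: "Diagnostic yield of cryobiopsy will be calculated as the proportion of patients for which cryobiopsy led to a specific diagnosis". None of the three makes an exception by indication, and the benign diagnoses listed in 3.6 and 5.4.3 (granuloma, inflammation, fibrosis, infection) do not include an adequate specimen without rejection.

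Surveillance patients are expected. Section 2.1 lists the indications as "lung transplant rejection surveillance, lung nodule biopsy, diffuse parenchymal lung disease, pneumonitis". Section 2.4 requires a lung transplantation center at every site. Section 3.4 sets a separate minimum of five biopsies for surveillance and cites a guideline standard of at least five pieces of expanded alveolar tissue for judging acute rejection. There is no quota by indication; section 2 says "Consecutive patients who have been referred for transbronchial biopsy by their treating pulmonologists will be enrolled".

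Section 5.2 describes the intended output as "diagnostic yield across various disease states necessitating transbronchial biopsy" and adds "This descriptive data will be crucial in the planning of future clinical trials".

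**The concern.** In a nodule or in diffuse disease, normal lung on histology means that the biopsy did not explain the abnormality, so calling it non-diagnostic is reasonable. In rejection surveillance the question is whether rejection is present, and adequate tissue that shows none has answered it. Section 3.6 treats both cases alike.

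There are two consequences. First, the yield that can be attained falls with every adequate rejection-free surveillance patient, however well the probe performs. Second, if yield among surveillance patients differs from yield in the other indications, the overall figure moves with their share. That share is whatever consecutive referral produces.

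At stake is how useful the figure is for planning later trials, the use that 5.2 names. A later trial in nodules or diffuse disease could not take a planning value from an overall yield that mixes in an unstated number of surveillance patients.

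**Working it through.** The documents state no expected or target yield, so there is no figure of the plan to reproduce. The only fixed number is the sample size of 50 (section 5.7).

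**Inputs**
- n = 50, taking all 50 participants as analysed. Section 2.5 limits the analysis population to patients with at least one cryobiopsy attempt, so n could be slightly smaller.
- s, the surveillance share: not in the documents; assumed 10-60%.
- a, the share of surveillance patients whose biopsy is adequate and normal: not in the documents; assumed 50-90%.
- d, surveillance yield under the 3.6 rule: at most 1 - a, hence 0-50% over the assumed range of a.
- y, yield in the other indications: illustrated by 34% and 58%, the ends of the forceps range for diffuse disease in section 1. These are not cryobiopsy yields.

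**Step 1: ceiling on yield.** Each adequate rejection-free surveillance patient adds 0 to the numerator and 1 to the denominator, so the maximum falls by 1/50 = 2 points. With 10 surveillance patients and a = 70%, seven are normal and the ceiling is (50 - 7)/50 = 86%. With 20 surveillance patients it is (50 - 14)/50 = 72%. This holds even if every other biopsy is diagnostic.

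**Step 2: effect of leaving all surveillance patients out.** Overall yield is (1 - s)y + s d. Without surveillance patients it is y. The change is y - [(1 - s)y + s d] = s(y - d).

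| s | y | d | change s(y - d) |
|---|---|---|---|
| 60% | 34% | 50% | 0.6 x (-0.16) = -9.6 points |
| 60% | 58% | 0% | 0.6 x 0.58 = +34.8 points |
| 30% | 34% | 30% | 0.3 x 0.04 = +1.2 points |
| 30% | 58% | 0% | 0.3 x 0.58 = +17.4 points |

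The sign is that of y - d. It turns negative when surveillance yield exceeds yield elsewhere.

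**Step 3: case mix alone.** If s moves from 10% to 60% with y and d fixed, overall yield changes by 0.5(d - y). The extremes are 0.5 x (0.50 - 0.34) = +8 points and 0.5 x (0 - 0.58) = -29 points. If s moves only from 20% to 40% at a = 70% (d = 0-30%), the change is 0.2(d - y), from 0.2 x (0.30 - 0.34) = -0.8 to 0.2 x (0 - 0.58) = -11.6 points.

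**Step 4: precision, for scale.** Clopper-Pearson 95% intervals are 35.5-64.5% for 25/50 (half-width 14.5 points), 27.2-72.8% for 10/20 and 18.7-81.3% for 5/10. The case-mix effect can therefore be well below or above sampling error in the overall figure.

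**The case against.** The strongest reply is that the definition is strict, stated in advance and applied consistently. Section 2.3 asks for a specific histologic diagnosis, and a normal biopsy does not provide one. The protocol never equates yield with answering the clinical question. Section 5.2 already intends yield by disease state, and the silence of 5.4.3 does not contradict it. Whether tissue could be assessed is measured separately by the core-lab grade. Indication is largely recoverable from the radiographic data in 3.6 and the surveillance minimum in 3.4, so the split could be made at analysis. The endpoint is descriptive, and 5.1 disclaims statistical conclusions.

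Most of this stands, and it limits the importance of the point. It does not remove it. A split alone would leave normal surveillance biopsies scored as non-diagnostic, the core-lab grade is not linked to yield, and the choice of denominator for the overall figure is better made before results are seen. The word across in 5.2 could mean pooled over disease states; yield by disease state is the more natural reading, and the scoring problem remains under either.

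Three stronger readings are tempting and not supported:
- A reader might infer that only an overall yield will be reported. The documents do not say so.
- A reader might take s x a, which is 5 points (0.10 x 0.50) to 54 points (0.60 x 0.90) on the assumed ranges, as the error in the planned yield. That product is the gap to a different endpoint, one that counts rejection-free biopsies as answers. It is not the effect of leaving surveillance patients out.
- A reader might remove only the rejection-free patients. At y = 58% and a = 70%, taking d = 30%, that raises yield by 8.5 points with 10 surveillance patients (60.9% against 52.4%) and by 18.2 with 20 (65.0% against 46.8%). This is exclusion by outcome and raises yield by construction. Removing all surveillance patients gives 5.6 and 11.2 points.

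**Conclusion.** The point holds as a gap in the definition and analysis of a secondary endpoint. Under 3.6 and 5.4.3 as written, an adequate rejection-free surveillance biopsy counts as non-diagnostic, and the overall yield depends on an uncontrolled surveillance share. The loss of 2 points of attainable yield per such patient follows from the text and n = 50 alone.

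The net effect on the reported yield is not established in size or direction. The range of -9.6 to +34.8 points rests wholly on assumed values of s and d and on forceps yields borrowed for y; at s = 30% with d = 0-30% it is +1.2 to +17.4 points. The documents therefore do not support a claim that the planned yield is understated by a known or large amount.

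Severity is minor. No threshold or decision rule uses yield, and the primary safety result is unaffected.

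**What to change.** In 5.4.3:
1. Report diagnostic yield by indication, as n/N with exact 95% confidence intervals, under the existing 3.6 rule.
2. Show the overall yield with and without all surveillance patients, not only the rejection-free ones.
3. For surveillance patients, report assessability separately from the planned core-lab grades: for example, the number of specimens per patient graded 3-6 (the grades at which assessment is possible) and the proportion of patients with at least five such specimens, in line with the five-piece standard cited in 3.4. Do not use a best-grade rule, under which a single grade 3 specimen would make the whole patient assessable.
4. Add indication as an explicit field on the case report form; 3.6 does not list it.

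The cost is SAP wording and one form field. Surveillance status must already be known for each case because 3.4 sets its own biopsy minimum, and the core-lab grade is already a secondary endpoint. Design, sample size and procedures do not change. The downside is small strata: 5/10 gives 18.7-81.3%, so the results by indication should be labelled descriptive only.

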3.7. Adverse Events and Serious Adverse Events

3.7.1. Adverse Events

An adverse event (AE) is any untoward medical occurrence, unintended disease or injury, or untoward clinical signs (including abnormal laboratory findings) in subjects, users or other persons, whether or not related to the investigational medical device. Note: Pre-existing conditions are not considered to be adverse events unless there is a change in the nature or severity of the condition.

3.7.2. Serious Adverse Event

A serious adverse event (SAE) is an event that has:

- 1) Led to death,
- 2) Led to serious deterioration in the health of the subject, that either resulted in
 - a life-threatening illness or injury, or
 - a permanent impairment of a body structure, or
 - in-patient or prolonged hospitalization, or
 - medical or surgical intervention to prevent life-threatening illness or injury or permanent impairment to a body structure or a body function,
- 3) led to fetal distress, fetal death or a congenital abnormality or birth defect

Note: Planned hospitalization for a pre-existing condition, or a procedure required by the study, without serious health deterioration is not considered a SAE.

3.7.3. Adverse Event Relationship

The PI will assess the relationship of an adverse event to the device and/or procedure as follows:

- *Not Related:* No relationship appears to exist between the AE and the device and/or procedure
- *Related:* The AE follows a plausible temporal sequence following administration of the study device or execution of the procedure.

- *Undetermined*: It is not possible to determine the relationship of the AE with the study treatment.

3.7.4. Adverse Event Outcome

The outcome of AEs will be recorded as follows:

- *Resolved*: The event is considered fully resolved.
- *Continuing*: At study exit the event is considered ongoing. Note: Any unresolved AE ongoing past study exit will be monitored by the physician per institutional standard of care.

3.7.5. Adverse Event Recording

AEs will be documented in the applicable source documentation (i.e. medical record). As possible, study data collection forms should capture the event diagnosis as opposed to symptoms (e.g. Infection vs. fever). The adverse events of pneumothorax and bronchopulmonary hemorrhage (including hemoptysis) will be documented as follows:

Pneumothorax: Pneumothorax will be documented by both post-biopsy CXR and chest ultrasonography. Pneumothorax severity and required intervention, such as chest tube placement, will be recorded. Severity will be classified according to Common Terminology Criteria for Adverse Events (CTCAE) grade as follows:

- *Grade 1*: Asymptomatic; clinical or diagnostic observation only; intervention not indicated
- *Grade 2*: Symptomatic; intervention indicated (e.g. tube placement without sclerosis)
- *Grade 3*: Sclerosis and/or operative intervention indicated; hospitalization indicated.
- *Grade 4*: Life-threatening consequences; urgent intervention indicated
- *Grade 5*: Death

Bleeding: Bleeding will be categorized on an adapted grading system.¹² The grades are as follows:

- Grade 0: No bleeding or only traces of blood not requiring suctioning
- Grade 1: Bleeding requiring suction to clear
- Grade 2: Bleeding requiring wedging of the biopsied segment with the flexible bronchoscope and/or iced saline
- Grade 3: Bleeding requiring inflation of a bronchial blocker
- Grade 4: Bleeding causing cardiopulmonary instability

3.7.6. SERIOUS ADVERSE EVENT REPORTING

A Serious Adverse Event is defined as the occurrence of bleeding grade ≥ 3 (see Adverse Events for bleeding grading system), pneumothorax requiring chest tube placement (Grade ≥ 2 , see Adverse Events for pneumothorax grading system), post-procedure respiratory failure defined as the need for non-invasive or mechanical ventilation requiring ICU admission, or death, which have occurred within 30 days after procedure, respectively.

All device and/or procedure related adverse events will be reported. Device related events will be collected from initiation of the index procedure (insertion of the cryoprobe into the working channel of the bronchoscope), intra-procedure, and during the standard of care follow-up period of 30 days. 30 day follow up will be assessed by chart review, if data is not able to be extracted by chart review a phone call will be made to assess any adverse events that may have occurred. Study sites are responsible to report adverse events and complications to their IRBs according to institutional requirements.

The study clinician at the site will complete a SAE Form within the following timelines:

- All deaths and immediately life-threatening events, related to the device or the procedure will be recorded on the SAE Form and submitted to the DSMB/study sponsor, lead coordinating center, and device manufacturer within 24 hours of site awareness.
- Other SAEs will be submitted to the DSMB/study sponsor and lead coordinating center within 72 hours of site awareness.

All SAEs will be followed until satisfactory resolution or until the site investigator deems the event to be chronic or the adherence to be stable. Other supporting documentation of the event may be requested by the DSMB/study sponsor and should be provided as soon as possible. The study sponsor will be responsible for notifying FDA of any unexpected fatal or life-threatening suspected adverse reaction as soon as possible but in no case later than 7 calendar days after the sponsor's initial receipt of the information.

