Population:	
Inclusion Criteria:
 
 • Male or Female, \geq 18-years-old • Scheduled to undergo bronchoscopy with transbronchial biopsy as the standard medical care determined by their treating pulmonologist 
Exclusion Criteria:
 
 • Pregnant or nursing females, or females of child bearing potential who refuse to take a pregnancy test prior to enrollment • Individuals with current or recent systematic conditions, such as uncontrolled hypertension (systolic $>$ 200 mmHg or diastolic $>$ 110 mmHg), type 1 diabetes, severe pulmonary hypertension, acute kidney injury, stroke (within the last 6 months) or myocardial infarction (within the last 3 months) • Presence of bleeding disorder • Platelet count $<$ 50,000 • Current use of systemic anticoagulation or antiplatelet therapy without the ability to hold therapy for the recommended amount of time prior to an invasive procedure (aspirin monotherapy is acceptable)

	
 • International Normalized Ratio (INR) <1.5 • Robotic Bronchoscopy • Do Not Resuscitate (DNR) status • Do Not Intubate (DNI) status
Endpoints:	
The primary endpoint will be the number of serious adverse events in those enrolled in the study. Serious adverse events are defined as:
 
 • Grade 3 or 4 bleeding • Pneumothorax requiring chest tube placement (Grade ≥ 2) • 30-day respiratory failure and death. 
Secondary endpoints include minor adverse events (bleeding Grade 1 or 2), pneumothorax not requiring chest tube placement (Grade 1), histologic accessibility, diagnostic yield

Statistical Methodology	This study is designed to ensure the serious adverse event rate using the 1.1mm flexible single-use cryoprobe with oversheath will not exceed the expected serious adverse event rate of transbronchial biopsy using standard biopsy procedures (30%)
Safety Monitoring	After each 10 consecutive patients are enrolled, the DSMB will review safety. Additionally, after each serious adverse event, the study will be halted until adjudicated by the DSMB.

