2.2. PRIMARY SAFETY ENDPOINT

The primary safety outcome will be the proportion of participants enrolled that underwent a device related Serious Adverse Events. A complication will be considered 'device related' if it occurs following the index procedure of an attempt at cryoprobe insertion into the working channel of the bronchoscope.

A device related Serious Adverse Event is defined by the presence of any of the following:

- bleeding grade ≥ 3 (see Adverse Events for bleeding grading system)
- pneumothorax requiring chest tube placement (Grade ≥ 2 , see Adverse Events for pneumothorax grading system)
- post-procedure respiratory failure defined as the need for non-invasive or mechanical ventilation requiring ICU admission within 30 days after procedure
- Death within 30 days after procedure

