3.9. STUDY HALTING RULES

Any SAE will serve as a stopping rule. The DSMB will convene to adjudicate the event. Enrollment will resume if the SAE is adjudicated by the DSMB. Additionally, if the SAE rate rises above 30% for two consecutive batches (10 cases per batch), the study will be halted.

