5.6. SAFETY REVIEW

After any serious adverse event, a safety review will take place and recruitment at all sites will be halted. The DSMB will meet to review the case and overall safety of the trial, once adjudicated by the DSMB, the trial can be resumed.

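### Serious adverse event is defined in two ways, and the rule that halts the trial after a single event does not say which definition applies

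*Combined protocol and SAP*

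**What the plan says.** **Definition A (3.7.2).** An SAE is an event that led to death, to fetal harm, or to a serious deterioration in health with one of several results. One of those results is "in-patient or prolonged hospitalization". The section excludes planned admissions without serious deterioration, and 3.7.1 excludes pre-existing conditions that have not changed.

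**Definition B (3.7.6).** Here "A Serious Adverse Event is defined as the occurrence of bleeding grade" 3 or above, pneumothorax requiring a chest tube, respiratory failure requiring ventilation and ICU admission, or death, each within 30 days. The synopsis (Endpoints row) and 5.4.2 give the same composite.

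**The single-event halt**, stated three times without a cross-reference:
- 3.9: "Any SAE will serve as a stopping rule. The DSMB will convene to adjudicate the event".
- 5.6: "After any serious adverse event, a safety review will take place and recruitment at all sites will be halted".
- Synopsis, Safety Monitoring: "Additionally, after each serious adverse event, the study will be halted until adjudicated by the DSMB".

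**Reporting (3.7.6).** Related deaths and immediately life-threatening events go on the SAE Form within 24 hours of site awareness. Other SAEs go to the DSMB/sponsor and the lead coordinating center within 72 hours. The DSMB also reviews safety after every 10 patients (3.8, 5.5).

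**The concern.** A halting rule works only if those applying it can tell which events set it off. This one depends on a term that the protocol defines twice, with different contents, and nothing ranks the two definitions. They part company over serious harms that the procedure is known to risk but that the composite leaves out. Section 1.4 lists pneumonia, empyema and thromboembolism among those risks.

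At stake is whether recruitment continues while a serious related harm awaits review. Safety is the objective of the trial, which 1.4 presents as the first dedicated human safety study of this probe, although the device is already cleared and the study is post-market. The opposite error also matters: read literally, 3.7.2 would stop all sites for any serious admission, including one judged unrelated.

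**Working it through.** **Step 1. One test case under both definitions.** A patient develops a procedure-related pneumonia within 30 days, deteriorates seriously and is admitted. There is no ICU ventilation, no chest tube, no grade 3 or 4 bleeding, and the patient survives. An empyema or thromboembolism can be followed through in the same way.

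| | 3.7.2 governs | 3.7.6 governs |
|---|---|---|
| Is it an SAE? | Yes | No |
| Single-event halt (3.9, 5.6, synopsis) | All sites stop until the DSMB adjudicates | None |
| Route to the DSMB | SAE Form within 72 hours, or 24 if immediately life-threatening | AE reporting, REDCap access (11.1), the next 10-patient review, or the 24-hour form if immediately life-threatening |
| Counted in the primary endpoint (5.4.2) | No | No |

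The two readings give opposite answers on the halt and the same answer on the primary endpoint.

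**Step 2. Enrolment pace.** Inputs: 50 participants (5.7) and a 3-month enrolment period (2.4). Assumptions: 90 days and even enrolment.
- 90 / 50 = 1.8 days per patient.
- 10 × 1.8 = 18 days per batch of 10.

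**Step 3. Composite reading: patients enrolled before the next scheduled review.** If the event becomes known at a random point within a batch, the number still to enrol is 0, 1, …, 9, equally likely.
- Mean: (0 + 1 + … + 9) / 10 = 45 / 10 = 4.5 patients, or 4.5 × 1.8 = 8.1 days.
- Maximum: 9 patients, or 9 × 1.8 = 16.2 days.

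This takes the review at each tenth enrolment (3.8). If it waits for completed cases, as 5.5 says, the delay is longer.

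**Step 4. 3.7.2 reading: patients enrolled before a halt.** The 72-hour window is 3 days, so up to 3 / 1.8 = 1.67, about 1.7 patients. The contrast is therefore a mean of 4.5 (range 0 to 9) against at most about 1.7, not against zero.

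**Step 5. How often would this arise?** The documents give no rate for SAEs that meet 3.7.2 but lie outside the composite. For scale only, with an assumed rate r per patient, the expected number is 50r and the chance of at least one is 1 − (1 − r)^50.

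| Assumed r | Expected in 50 | Chance of at least one |
|---|---|---|
| 1% | 0.5 | 39.5% |
| 2% | 1.0 | 63.6% |
| 5% | 2.5 | 92.3% |
| 10% | 5.0 | 99.5% |

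These figures restate the assumption and are not evidence about the probe.

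**The case against.** The strongest reply is that context already points to the composite. The synopsis defines SAEs as the four events in the same table that states the halt. Section 3.7.6 is the last definition before 3.9, and 5.4.2 is the only one in Section 5, ahead of 5.6. Section 3.9 also uses the term for the 30% batch rule, whose threshold comes from bleeding and pneumothorax data. All of this stands, and the composite may well be what was intended. It does not close the question, because on that reading the full definition in 3.7.2 governs no halt, and no section says so. The DSMB charter (3.8) is to define the data elements the board needs, but it was not yet written and does not promise to define the trigger.

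It is also fair to say that the event would not be hidden. Related AEs must be reported (3.7.6), AEs are entered in REDCap, to which the DSMB has access (11.1), and there are monthly central assessments (Section 4). Only the immediate halt is in doubt.

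Three stronger readings are tempting but unsupported:
- **That a pneumothorax managed without a tube shows the same conflict.** Section 2.3 confines that secondary endpoint to Grade 1, which 3.7.5 defines as asymptomatic and observation-only. That is not a serious deterioration. The pneumothorax counts in Table 1 therefore give no anchor for the frequency of the events at issue.
- **That 2.2 implies a wider class of SAEs.** It says "A device related Serious Adverse Event is defined by the presence of any of the following", but it defines device related by timing after attempted probe insertion, so the qualifier does not point to other event types.
- **That the site itself must trigger the halt.** The documents do not say this. SAEs go to one coordinating center and one DSMB.

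**Conclusion.** The point holds as a contradiction within a safety rule. One term has two definitions, the single-event halt cites neither, and a foreseeable class of serious, procedure-related, non-fatal harms halts all sites under one and none under the other. It should be corrected, though its reach is limited.

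The size is a mean of 4.5 further patients (range 0 to 9, about 8 days on average and 16 at most) before the next scheduled review on the composite reading, against up to about 1.7 before a halt on the 3.7.2 reading. This rests on even enrolment over 90 days, review at each tenth enrolment and use of the full 72-hour window. The frequency of such events is unknown.

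A reader might infer that the trial's conclusion on safety is compromised. It is not: 5.4.2 lists the events in the primary criterion explicitly, and the 30% rule is tied to the composite by the origin of its threshold.

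**What to change.** 1. Call the four-event composite the *primary safety event* in the synopsis, 2.2, 3.7.6, 5.2 and 5.4.2. Keep SAE for the 3.7.2 definition, and state in 3.7.6 that the SAE Form covers both.
2. In 3.9, 5.6 and the synopsis, state that the halt follows any primary safety event, and any other 3.7.2 SAE rated Related or Undetermined under 3.7.3. Other SAEs rated Not Related go to the DSMB by the 72-hour route without a halt.
3. In 3.9 and 5.5, apply the two-batch 30% rule and the interim rate to primary safety events only.

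A single sentence naming the governing definition would remove the ambiguity. It would leave either related serious harms outside the halt or unrelated admissions inside it, and item 2 avoids both.

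**Cost.** Wording changes and an IRB amendment, with no new patients, visits or data. Compared with the composite reading there may be a few short extra halts in a 3-month enrolment, because 3.7.3 counts an event as Related on plausible timing alone. If every such event were rated Related or Undetermined, the assumed rates of 1% to 10% would mean about 0.5 to 5 extra halts.
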